## **4. Primary Outcome Measure:**

EEG Results: Evoked Brain Potentials (measured brain response that is the direct result of a specific cognitive event). We will be analyzing change from baseline EEG results at 8 weeks (before and after the subject takes the flibanserin or placebo). We will average the electrical brain activity evoked by each type of stimuli to calculate the evoked brain potentials (any stereotyped electrophysiological response to a stimulus).

Evoked brain potentials in response to sexually desired stimuli compared to:

1. Non sexually desired stimuli
2. Basic visual non-sexual stimuli (reversal checkerboard) will be our proposed endpoints, as they will allow us to measure electric brain signals specific to cognitive

mechanisms underlying sexual stimuli processing rather than any other non-cognitive processes or basic visual processes. Amplitude of the signal, latency, and brain topography across 128 recorded vectors will be measured.

### **Secondary Outcome Measures:**

- Eye movement tracking: movements to first saccades. We will be analyzing change from baseline eye movement tracking results at 8 weeks.
- Female Sexual Function Index: change from baseline to final score at 8 weeks.
- UCLA Loneliness Scale: change from baseline to final score at 8 weeks.
- Life Satisfaction Scale: change from baseline to final score at 8 weeks.
- Body Dysmorphic Disorder Questionnaire: change in answers from baseline to final visit at 8 weeks.
- Hamilton Anxiety and Depression Scale: change from baseline to final score at 8 weeks.
- Rosenberg Self-Esteem Scale: change from baseline to final score at 8 weeks.
- Hostility Measure: change from baseline to final score at 8 weeks.
- Female Sexual Distress Scale-Revised: change from baseline to final score at 8 weeks.
- IOS Scale with Partner: change in answers from baseline to final answers at 8 weeks.
- Body image measure: change in baseline to final score at 8 weeks.
- Sexual Desire Inventory: change in baseline to final score at 8 weeks.
- Marital Satisfaction Scale: change in baseline to final score at 8 weeks.

### **5. Methodology:**

The proposed study aims to test 60 pre-menopausal heterosexual or bisexual women (i.e., women who are menstruating) and 60 postmenopausal heterosexual or bisexual women (women who are no longer menstruating for at least 6 months) with hypoactive sexual desire disorder (HSDD) and investigate how their brain activity (as measured by non-invasive surface electroencephalogram, EEG) responds to desirable stimuli (photographs of models in business suits) before and after the administration of an FDA approved drug, Addyi (ingredient Flibanserin, NDA# 022526) for sexual desire disorder. The goal of this experiment is to investigate how the subjects' brain waves and their subjective desire for sexual activity change after an 8-week intake of Addyi

(Flibanserin; 100mg **at bedtime**)—an FDA approved drug for the treatment of hypoactive sexual desire disorder (HSDD) in **premenopausal women (but not FDA approved in postmenopausal women)** or after an 8-week intake of a placebo. The pharmacist will randomly assign once the subject to the treatment group (group with Flibanserin) or to the control group (group with placebo). Before and then again after the 8-week regimen, the patient will be asked to fill-out a series of questionnaires (e.g., demographics, body image; sexual desire) and do a behavioral visual task on a computer while the patient's brain activity (brain waves) and eye-movement will be recorded using a non-invasive high-density electroencephalogram (EEG) system and a non-invasive eye-tracking system, respectively. At mid-term (at 4 weeks), the patient will be also asked to fill-out the same series of questionnaires (e.g., demographics, body image; sexual desire) and do the same behavioral visual task on a computer while the patient's brain activity (brain waves) and eye-movement will be recorded using a non-invasive high-density electroencephalogram (EEG) system and a non-invasive eye-tracking system, respectively.

Subjects will be recruited via Flyers posted on Campus and/or in Obstetrics and Gynecology practices and/or via ads posted on Craigslist by research coordinator, [name]. From these ads, interested individuals will be asked to go on Survey Monkey (<https://www.surveymonkey.com/r/HPENlabresearch>) and complete a survey that will help us determine whether they meet our selection criteria or email [name] at [[contact]](mailto:[contact]) or call the research team. Research coordinator will then contact individuals who may meet selection criteria. She and [name] and/or [name] will meet with them and give them the informed consent to read and go through it with the subjects. Upon receipt of a signed informed consent, participants will meet with [name] or [name] who will diagnose them with HSDD. If the subject does not have HSDD, she is not eligible to participate in the study. Subjects with a confirmed diagnosis of HSDD by [name] or [name] will then be randomly assigned by the UChicago Pharmacy/Investigational Drug Service to either Addyi (100 mg once daily at bedtime for 8 weeks, n = 60 subjects) or placebo (100 mg once daily at bedtime for 8 weeks, n = 60 subjects). The research question of this double-blind randomized outpatient clinical trial is to determine the pre-post change in the Flibanserin group and investigate the

extent to which Flibanserin normalizes brain activity in women with HSDD and the extent to which regional brain activation is associated with changes in symptoms and behavior (as measured with self-report measures of sexual desire and/or eye-tracking movements).

The study is registered on clinicaltrials.gov.

## **6. Duration of Protocol:**

The total duration of the entire study on campus is 4.5 hours maximum. **Visit 1's duration:** 2 hours. Upon receipt of the subject's written consent, the subject will meet with [name] or [name] to have a diagnosis of HSDD confirmed, take a urine pregnancy test, and be asked to fill out questionnaires (duration 45 minutes maximum). Then, an IRB-approved member of the HPEN laboratory will walk the subject to the laboratory where the subject will be completing other questionnaires and performing the behavioral visual task while the subject's brain activity and eye movements are recorded (1h15 minutes maximum, including breaks and time to walk to the laboratory). At the end of Visit 1, a member of the HPEN laboratory will walk the subject to the pharmacy where they will receive either Flibanserin or Placebo. The HPEN member will not know what the patient receives (placebo or Flibanserin). One week after visit 1, a member of the study staff will contact the subject via telephone to see if the subject has experienced any side effects or if the subject has any questions. If any side effects are reported, the study staff will immediately contact [name] or [name] to confirm that any appropriate follow up is provided. **Phone call 2's duration:** 30 minutes. Two weeks after visit 1, the subject will be asked about any side effects she has experienced or is currently experiencing. The subject will also be asked to fill out some of the same questionnaires as visit 1 and answer questions about mood and sexual desire. **Visit 2's duration:** 1 hour. The subject will go directly to the HPEN laboratory, where the subject will perform the behavioral visual task again while the subject's brain activity and eye movements are recorded and fill out the same questionnaires the subject filled out during Visit 1. **Visit 3's duration:** 1 hour. The subject will again go directly to the HPEN laboratory to perform the behavioral visual task while the subject's brain activity and eye movements are recorded and fill out the same questionnaires as Visits 1 and 3.

## **8. Special Precautions:**

Precautions related to the contradictions of Addyi (Flibanserin) will be followed. This will occur in the survey monkey pre-screening survey and again in the consent form.

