## **11. Statistical Analyses:**

EEG data will be analyzed using an established Matlab toolbox, CENA (The Chicago Electrical Neuroimaging Analytics). Standard statistical analyses will be performed using SPSS. Compared to fMRI, which has a very low temporal resolution, high-density EEG/ERP has a very high temporal resolution ([name] & Bianchi-Demicheli, 2008). When combined with brain source localization algorithms, high-density EEG-ERP is called electrical neuroimaging. Electrical neuroimaging can identify dynamical patterns of communication between brain regions that contrast analyses, such as fMRI, may not detect. This proposal takes advantage of electrical neuroimaging and a new suite of tools (i.e., the Chicago Electrical Neuroimaging Analytics, CENA), that [name] developed and validated recently for segmenting high-density electrical brain activity (Cacioppo et al., 2014, 2015). Compared to the standard waveform analysis of event-related potentials (ERP) components that provide local information about amplitude and latency of the brain electric signal collected from one electrode in response to a stimulus, CENA provides general information about the stable momentary configuration of the global scalp electric potential over a high-density multi-channel electrode array. This approach provides information about the temporal sequence of discrete information processing operations evoked by the presentation of a stimulus within the context of a particular experimental task. That temporal sequence of information processing includes a series of stable brain microstates, each of which is characterized by specific cognitive computations and a relatively stable spatial distribution of brain activity. Combined with brain source localization algorithms, this method can then provide a video-clip of the potential brain sources that sustain every electrical brain state recorded from the surface of the scalp –without having to perform an fMRI scan (see attached example). The brain microstate approach complements the traditional approach of ERP peaks and troughs at specific electrode positions, but with more comprehensive analyses of time-varying activity across the entire scalp (Cacioppo et al., 2014, 2015).

Subjects who do not adhere to the recommended dosing regimen will not be discontinued from the study. Rather, data from these subjects should be included in an intent-to-treat analysis.

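### As described, the alcohol and interacting-medicine precautions are checked only before the first tablet; none of the four later contacts is said to ask about either exposure during the 8 weeks of dosing.

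*Combined protocol and SAP*

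**What the plan says.** Section 8 gives the timing of the precautions that follow from the contraindications: "This will occur in the survey monkey pre-screening survey and again in the consent form". Section 23 adds entry criteria. It excludes women who say they cannot stop drinking, women currently on interacting medicines, and women with substance abuse or dependence in the past 3 months. Section 25 has the physician decide eligibility at Visit 1, after which all 56 tablets are dispensed together.

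Section 12 lists alcohol and moderate or strong CYP3A4 inhibitors as contraindications. By signing consent the woman agrees to avoid alcohol for 8 weeks, and she is asked to tell the team if she feels unable to do so. Section 27 lists prohibited medicines without a schedule for re-checking them.

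Section 6 describes four contacts after dispensing:

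- The week-1 call is to "see if the subject has experienced any side effects or if the subject has any questions".
- For the second call: "Two weeks after visit 1, the subject will be asked about any side effects she has experienced or is currently experiencing". Some questionnaires and questions on mood and desire follow.
- For Visit 2, placed at 4 weeks by Section 5: "The subject will go directly to the HPEN laboratory, where the subject will perform the behavioral visual task again".
- For Visit 3, at 8 weeks: "The subject will again go directly to the HPEN laboratory to perform the behavioral visual task".

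Questionnaires are repeated at both visits. Section 13 adds vital signs with orthostatic readings at every visit and tells women to call about side effects. Section 24 counts returned tablets. Section 28 makes study staff responsible for detecting and recording all adverse events.

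**The concern.** The restrictions matter while the woman is taking the drug, but every described check comes before she starts. Section 12 links alcohol taken with flibanserin to serious hypotension and syncope, and gives this as the reason the drug is supplied only under a REMS programme. A woman who starts drinking again in week 3, or is prescribed an interacting antibiotic or antifungal, meets no described question that would bring it to light while she still has tablets. Dispensing everything at once also removes the refill visit at which such a question would naturally be asked.

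Patient safety is what is at stake. Orthostatic readings at Visits 2 and 3 may pick up a consequence; they do not reveal the exposure, which is the part that can be stopped. Section 12 also notes that alcohol use went unrecorded in the five earlier premenopausal trials it summarises, so the adverse-reaction rates quoted there do not show how the drug behaves with known alcohol use.

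**Working it through.** The plan gives no figure of its own on this point, so the check sets each contact against each question and then counts days and tablets.

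**Inputs.** 56 tablets, one a day, all dispensed at Visit 1 (Section 25). Calls at weeks 1 and 2 (Section 6). Visit 2 at 4 weeks and Visit 3 at 8 weeks (Section 5). Sample size 120 (Section 10). Assumptions: dosing starts on the evening of Visit 1, no dose is missed, and contacts fall on days 7, 14, 28 and 56.

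**Step 1: what each contact is described as asking, and tablets left (56 minus days elapsed).**

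| Contact | Day | Alcohol or new medicine | Side effects | Tablets left |
|---|---|---|---|---|
| Week-1 call | 7 | not described | yes | 56 − 7 = 49 |
| Week-2 call | 14 | not described | yes | 56 − 14 = 42 |
| Visit 2 | 28 | not described | not described | 56 − 28 = 28 |
| Visit 3 | 56 | not described | not described | 56 − 56 = 0 |

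Alcohol or medicine question: 0 of 4 contacts. Side-effect question: 2 of 4.

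**Step 2: longest stretch of dosing without a described alcohol or medicine question.**

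- As written: from Visit 1 to day 56, that is 56 − 0 = 56 days.
- With a question at every contact: gaps of 7 − 0 = 7, 14 − 7 = 7, 28 − 14 = 14 and 56 − 28 = 28 days. The longest is 28 days.
- Three of the four questions (days 7, 14 and 28) come while tablets remain. The day-56 question only completes the record.

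**Step 3: side effects, counted separately.** The last scheduled question is on day 14, leaving 56 − 14 = 42 days. Adding it at Visits 2 and 3 makes the longest gap 28 days. Only two questions are new here, and only the one at Visit 2 comes while tablets remain.

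**Step 4: do other provisions fill the gap?**

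- The Section 12 request to tell the team depends on the woman volunteering, reads mainly as an entry statement, and does not cover medicines.
- The exclusion for recent substance abuse lowers the risk at entry but does not observe drinking afterwards.
- Vital signs measure effects, not exposures.
- The pill count shows missed study doses only.
- Section 28 covers events, not exposures.

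None of these replaces a direct question.

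**The case against.** The strongest reply is that Section 6 is not a complete list of procedures. It leaves out the vital signs of Section 13 and the tablet return of Section 24, so its silence on alcohol is weak evidence that nobody asks. Section 5 says of the mid-term visit: "At mid-term (at 4 weeks), the patient will be also asked to fill-out the same series of questionnaires". The content of those questionnaires is given only by example. The consent form and two short parts of the protocol were not available, and the REMS programme, whose terms are not in the documents, exists because of alcohol. All of this stands. It limits the finding to what is described, and it means the remedy may turn out to be a cross-reference. It does not supply a described question, and none of the instruments named in Section 4 suggests one.

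Three stronger readings are tempting and should not be drawn.

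- A reader might infer that the missing side-effect question at Visits 2 and 3 distorts the comparison of adverse events between arms. The trial is double-blind and both arms have the same contacts, so no mechanism for imbalance is shown. The likelier result is some under-detection in both arms.
- A reader might infer that side effects go unwatched after week 2. Section 12 reports that most of the common reactions began within 14 days, a window both calls cover, and Sections 13 and 28 partly cover later weeks.
- A reader might take the 8-week period as stated for medicines too. It is stated for alcohol only. The medicine restriction during treatment rests on the Section 12 note contraindicating moderate or strong CYP3A4 inhibitors in patients taking the drug; Section 27 gives no duration.

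**Conclusion.** The point holds for alcohol and new medicines. On the text available, both are checked before the first tablet and at 0 of 4 later contacts, leaving up to 56 days of dosing without a described question about exposures the protocol itself contraindicates. The change would halve that to 28 days and put three questions at times when study drug can still be stopped. The side-effect part is a minor matter of completeness under Section 28, and no claim of imbalance between arms is made.

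This rests on the unseen consent form, questionnaires and REMS terms not already containing the questions, and on the stated schedule being followed. The documents give no rate of drinking or of new prescriptions during treatment, and none is assumed, so the number of women affected cannot be stated. The case for changing is a serious named hazard set against a very small cost.

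**What to change.** Amend Sections 6 and 8 so that at the week-1 call, the week-2 call and Visit 2, and at Visit 3 for the record, staff ask every participant about (1) any alcohol and (2) any new medicine since the last contact, noting the medicine's name. As a minor addition, put the existing side-effect question at Visits 2 and 3 as well.

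Section 6 already has a route to the physician: "If any side effects are reported, the study staff will immediately contact". Extend it to positive answers on alcohol and medicines. The physician should check new medicines against both Section 12 and Section 27, since ciprofloxacin, diltiazem and fluconazole are named only in the former. A match should lead to a decision on continuing study drug and not to an automatic stop: Section 12 lists oral contraceptives as interacting, while Section 22 accepts them as birth control. A woman taken off drug stays in follow-up. Section 11 already says of women who depart from the dosing regimen that "data from these subjects should be included in an intent-to-treat analysis", and the same rule should apply to her.

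Cost: a short amendment and a few minutes at contacts already scheduled. There are 120 × 4 = 480 contacts; at an assumed 2 to 3 minutes each, that is 480 × 2/60 = 16 to 480 × 3/60 = 24 staff hours over the whole study. The downsides are occasional physician decisions, some women stopping study drug, possible under-reporting of alcohol, and a remaining 28-day gap between Visits 2 and 3. If an existing questionnaire already asks these items, naming it in Section 8 is enough.

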## **9. Experimental Controls:**

We will recruit 60 pre-menopausal women and 60 postmenopausal women who have HSDD, as determined by one of the MDs on the research team (using the DSM 5 criteria), during Visit 1. Then, the pharmacist will randomly assign the subjects to the treatment group (group with Flibanserin) or to the control group (group with placebo).

## **10. Type and Number of Experimental Subjects:**

We expect to collect data from a total of 120 subjects between the age of 21 and 74 years. We will be testing premenopausal and postmenopausal women with hypoactive sexual desire disorder. Flibanserin is FDA approved for premenopausal but not postmenopausal women with HSDD. Women who are pregnant (or think they are pregnant), or who are nursing (or breastfeeding), or women who report not being able to stop drinking alcohol during the duration of the study will NOT be tested.

**Power:** Using G\* power calculation software (Version 3.1.9.2) for a within-between interaction in repeated measures ANOVA, a total sample size of 120 will yield 95% power to detect a significance, with alpha = .05 and an effect size of 0.14.

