and mechanism of missing data. A 2 (Treatment Type: Addyi or Placebo) x 2 (Group Type: pre- or post-menopausal) X 2 (type of stimuli: desired, nondesired) x 3 time (Visit 1, Visit 2, Visit 3) repeated-measures ANOVA will be performed on the reaction times and ratings to assess for main effects and interaction effects. P values, confidence interval, and effect sizes will be reported.

iii. Eye-tracking Data: A similar ANOVA will be performed for the following dependent variables: onset to first fixation and duration of fixation. As in our 2014's paper (Bolmont, Cacioppo, & Cacioppo), we will also analyzed include the subjects' visual area of interest (face vs. body) as a within-subject factors in our ANOVA.

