***Data from Five 24-Week, Randomized, Double-Blind Placebo-Controlled Trials in Premenopausal Women with HSDD***

The data presented below are derived from five 24-week randomized, double-blind, placebo-controlled trials in premenopausal women with acquired, generalized HSDD. In these five trials, the frequency and quantity of alcohol use was not recorded. Three of these trials (Studies 1 through 3) also provided efficacy data [see **Clinical Studies**]. One of these trials (Study 5) did not evaluate the 100 mg bedtime dose.

In four trials, 100 mg ADDYI at bedtime was administered to 1543 premenopausal women with HSDD, of whom 1060 completed 24 weeks of treatment. The clinical trial population was generally healthy without significant comorbid medical conditions or concomitant medications. The age range was 18-56 years old with a mean age of 36 years old, and 88% were Caucasian and 9% were Black.

Serious adverse reactions were reported in 0.9% and 0.5% of ADDYI-treated patients and placebo-treated patients, respectively.

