### **Adverse Reactions Leading to Discontinuation**

The discontinuation rate due to adverse reactions was 13% among patients treated with 100 mg ADDYI at bedtime and 6% among patients treated with placebo. Table 1 displays the most common adverse reactions leading to discontinuation in four trials of premenopausal women with HSDD.

**Table 1: Adverse Reactions\* Leading to Discontinuation in Randomized, Double-blind, Placebo-controlled Trials in Premenopausal Women with HSDD**

	PLACEBO (N=1556)	ADDYI (N=1543)
Dizziness	0.1%	1.7%
Nausea	0.1%	1.2%
Insomnia	0.2%	1.1%
Somnolence	0.3%	1.1%
Anxiety	0.3%	1%

\*Adverse reactions leading to discontinuation of > 1% of patients receiving 100 mg ADDYI at bedtime and at a higher incidence than placebo-treated patients.

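### The 95% power in Section 10 allows for no missing data: the 120 women recruited are also the 120 assumed to be analysed, and the inputs to the calculation are not stated

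*Combined protocol and SAP*

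**What the plan says.** Section 10 bases the sample size on a test "for a within-between interaction in repeated measures ANOVA" and concludes that "a total sample size of 120 will yield 95% power to detect a significance, with alpha = .05 and an effect size of 0.14". It does not give the number of groups, the number of measurements, the correlation between measurements or the sphericity correction, and it does not say on what scale 0.14 is measured.

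The same number appears at every stage:
- Recruitment, Section 9: "We will recruit 60 pre-menopausal women and 60 postmenopausal women who have HSDD".
- Randomisation, Section 5: 60 to Addyi and 60 to "placebo (100 mg once daily at bedtime for 8 weeks, n = 60 subjects".
- Data, Section 10: "We expect to collect data from a total of 120 subjects".

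Section 11 (Statistical Hypotheses, behavioural data) plans a repeated-measures ANOVA. Its between-subject part is "A 2 (Treatment Type: Addyi or Placebo) x 2 (Group Type: pre- or post-menopausal"), and its within-subject part is two stimulus types by three visits. A similar ANOVA is planned for eye-tracking. Section 11 keeps women who depart from the dosing regimen in the study and analyses them by intention to treat. For missing data it says only that the pattern and mechanism will be examined.

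Section 12 reports experience from earlier trials: "The discontinuation rate due to adverse reactions was 13% among patients treated with 100 mg ADDYI at bedtime", against 6% on placebo, and "1543 premenopausal women with HSDD, of whom 1060 completed 24 weeks of treatment". It adds that most of the common adverse reactions started in the first 14 days.

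**The concern.** Recruited, randomised, expected and powered numbers are all 120, so the planned loss is zero. Yet the document itself reports appreciable stopping on this drug, with most common reactions starting well inside the 8-week treatment period. The primary outcome (Section 4) is change in EEG from baseline to 8 weeks, so a woman who does not return at week 8 has no primary outcome. A standard repeated-measures ANOVA also drops any woman who misses one of its visits.

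If power is overstated, a null result will be given more weight than it deserves. Because the inputs are missing, a reader cannot tell how much margin the 95% contains.

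**Working it through.** **Inputs**
- From Section 10: N = 120, alpha = 0.05, effect size 0.14 (read as Cohen's f).
- From Section 11: k = 4 groups (treatment by menopausal status) and m = 6 measurements (2 stimuli by 3 visits).
- Assumed, because not stated: correlation rho = 0.5 and sphericity (epsilon = 1).
- From Section 12: 13% v 6% stopping for adverse reactions; 1060 of 1543 completing 24 weeks on flibanserin.

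**Formula.** For the within-between interaction, lambda = f² × N × m × epsilon/(1 − rho), df1 = (k − 1)(m − 1) × epsilon and df2 = (N − k)(m − 1) × epsilon. Power is the probability that a noncentral F with these values exceeds the central 5% critical value.

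**Step 1: the plan's own figure.** lambda = 0.0196 × 120 × 6/0.5 = 28.2, df 15 and 580, power 94.8%. Reaching 95% needs 121. The stated figure is therefore reproduced, but only with all 120 women.

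**Step 2: how many might have complete data**
- If stopping for adverse reactions meant losing data: 60 × 0.87 + 60 × 0.94 = 108.6, about 109 (9.5% loss).
- If the 24-week completion of 1060/1543 = 68.7% is scaled to 8 weeks at a constant rate (an assumption): 0.687^(1/3) = 0.882, and 120 × 0.882 = 105.9, about 106 (11.8% loss).
- Pessimistic bound, with the full 24-week flibanserin rate in both arms: 120 × 0.687 = 82.4, rounded up to 83.

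**Step 3: power at those numbers** (f = 0.14, rho = 0.5, epsilon = 1)

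| Women with complete data | 4 groups × 6 measurements | 2 arms × 2 times (baseline, week 8) |
|---|---|---|
| 120 | 94.8% | 86.0% |
| 109 | 92.1% | 82.6% |
| 106 | 91.1% | 81.5% |
| 83 (bound) | 80.3% | 71.2% |

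For the right-hand column at 120, lambda = 0.0196 × 120 × 2/0.5 = 9.41 with df 1 and 118.

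**Step 4: dependence on the unstated correlation** (power at 120 / 109 / 83)

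| rho | 4 × 6 | 2 × 2 |
|---|---|---|
| 0.3 | 82 / 77 / 62% | 73 / 69 / 57% |
| 0.5 | 95 / 92 / 80% | 86 / 83 / 71% |
| 0.6 | 99 / 97 / 90% | 93 / 90 / 80% |

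The layout matters as well. At rho = 0.5 and N = 120, 4 × 3 gives 80.4%, 2 × 3 gives 92.7% and 2 × 6 gives 99.3%.

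**The case against.** The strongest reply is that the Section 12 rates measure something else. They count stopping treatment, not missing an EEG visit. They cover 24 weeks rather than 8, and premenopausal women only, whereas half of this sample is postmenopausal. Section 11 expressly keeps women who do not follow the dosing regimen, and a woman who stops her tablets can still attend. All of this stands. The rates are upper guides, and a reader who infers that 31% of the data will be lost goes further than the documents allow. That figure comes from the flibanserin arm alone; placebo completion is not given. The intention-to-treat rule, however, supplies no measurement for a visit that did not take place, so it does not justify zero loss.

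Second, a reader might infer that 95% is miscalculated, or that it is reached only under the most generous assumptions. Neither is so. The figure reproduces at 94.8%. Other layouts or a higher correlation give more: 99.3% for 2 × 6 at rho 0.5, and 98.5% for 4 × 6 at rho 0.6. With rho 0.6, the 4 × 6 design stays above 95% even with 109 women. The recalculated powers are therefore conditional on rho, and the plan does not fix it.

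Third, the three-visit ANOVA is written for the behavioural and eye-tracking data. Section 11 names no such model for the EEG outcome, and for a comparison of baseline with week 8 a missed week-4 visit costs nothing. This also stands. It is why the two-time comparison is shown separately and why the number that matters most is the number of women with week-8 data.

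**Conclusion.** The concern holds as an unstated and optimistic assumption, not as an arithmetical error. With rho 0.5 and sphericity assumed, a loss of 9.5-12% costs about 3 to 4 points in the 4 × 6 design (94.8% to 91-92%) and about 3 to 5 points in the two-arm, two-time comparison (86% to about 82%). The pessimistic bound costs about 15 points in either.

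The documents do not support calling the trial seriously underpowered because of attrition. The larger uncertainty is in the missing inputs: at the full 120 and rho 0.5, power runs from 80% to 99% across the layouts 4 × 3, 2 × 3, 4 × 6 and 2 × 6.

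Sections 7 and 19 were not in the text available for review, so the absence of an attrition allowance refers to the remaining text. The point is worth correcting before the results are interpreted, and it does not call for a larger trial.

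**What to change.** 1. In Section 10, give the G*Power inputs: the scale of the effect size, number of groups, number of measurements, correlation and sphericity correction. State which comparison the figure refers to.
2. Restate the power at the number of women expected to have week-8 data, with the sponsor's own expected 8-week loss and its basis. Show a range over loss and correlation, in the form of the tables above.
3. In Section 11, replace the repeated-measures ANOVA with a mixed model for repeated measures on all randomised women, so that those who miss a visit still contribute. Name the model for the EEG change from baseline to week 8 in the same terms. State the missing-at-random assumption on which it rests. The model cannot replace week-8 information for women who have none.

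The cost is a few sentences and a slightly less favourable stated power. No additional patients or visits are needed.
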